- 10 12-Lead ECGs: Triplicate ECGs will accompany PK sampling as described in [Table 2](#). In addition, ECGs are to be performed as clinically indicated. Assessments will include an evaluation of heart rate, QT, and QTc intervals. RR interval should be recorded during each ECG assessment in order to calculate QTcF.
- 11 Disease Evaluations: To be performed at screening (28-day window allowed) and every 8 weeks from Cycle 1 Day 1 (\pm 10-day window for all other assessments except screening) until week 49 (~12 months) and then every 16 weeks. All on-study disease evaluations should be based on a calendar beginning from the first day of dosing. At screening/baseline, assessments are to include CT with contrast of the chest, CT or MRI of the abdomen and pelvis, as well as brain Magnetic Resonance Imaging (MRI) with and without gadolinium or CT with contrast, a whole-body bone scan (or PET or PET/CT if local standard for clinical trials) and evaluation of any superficial lesions. Subsequent disease assessments should include all sites of disease identified at base line or suspected to have developed; bone scans may be performed half as often (every 16 weeks) as other radiology evaluations and should be performed during assessment for confirmation of disease response. More detailed guidance on exceptional circumstances is provided in the protocol. Patients who discontinued the study for reasons other than objective disease progression will continue to have disease assessments at the same frequency until patient has radiologically confirmed progression, initiates a new anticancer therapy, or death.
- 12 Adverse Events: Serious Adverse Events (SAEs) will be reported from the time of informed consent until at least 28 days after the last administration of a study treatment. Adverse events will be reported from the first day of study treatment until at least 28 days after last dose of study drug, and until resolution or stabilization of acute adverse events and/or ongoing SAEs.
- 13 Long Term Follow-up: Survival status and subsequent therapies will be collected during long term follow-up every 2 months (\pm 14 days) from the End of Treatment Visit until death or lost to follow-up. Follow-up may be performed by telephone contact or email.

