9.2 Imputation of Alternative Cancer Treatment Start Date

If the start date is completely missing, given that the patient did receive the anti-cancer therapy, the start date will be set to last dose date + 1.

Missing Day Only

- If the month and year of the incomplete date are the same as the month and year of the last dose date, then the last dose date + 1 will be assigned to the missing day.
- If the month and year of the incomplete date are after the month and year of the last dose date, then the first day of the month will be assigned to the missing day.

Missing Month Only

- The day will be set as missing and treated as missing Day and Month.

Missing Day and Month

- If the year of the incomplete date is the same as the year of the last dose date, then the last dose date + 1 will be assigned to the missing day and month.
- If the year of the incomplete date is after the year of the last dose date, then Jan 1 will be assigned to the missing day and month.

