11.6 Efficacy Analyses and Efficacy Variables

11.6.1 Objective Response Rate (ORR)

Disease assessments involving radiographic evaluations may be performed over the course of a few days. The date of response (Complete Response, CR; Partial Response, PR; Stable Disease, SD; or Not Evaluable, NE) will be recorded as the date of the last radiographic evaluation included in the series for that time point assessment. The date of progression (PD) will be recorded as the date of the first radiographic evaluation included in the series for that time point assessment to identify progression.

ORR will be categorized in accordance with RECIST v1.1. (Appendix 3) Objective Response Rate (ORR) is defined as the percent of patients documented to have a confirmed CR or PR as defined in Table 9.

Descriptive statistics (frequency and percentage) for ORR, CR, and PR will be presented. The 95% exact Clopper-Pearson CI of these response rates will be calculated. An exact test for single proportion (two-sided $\alpha = 5\%$) will be performed to test $H_0: ORR \leq 5\%$ against $H_1: ORR > 5\%$.

Best overall response (BOR) is defined as the best response among all overall responses (in the order CR, PR, SD, PD, and indeterminate NE) recorded from the start of study drug until disease progression/recurrence, or start of anti-cancer therapy, whichever comes first.

The status of best response of CR or PR must be confirmed by repeat tumor assessment within no less than 4 weeks according to RECIST version 1.1. If the status of CR or PR cannot be confirmed by repeat tumor assessment, the BOR of unconfirmed CR and PR will be determined per RECIST 1.1. The status of BOR of SD requires an on-study assessment after at least 42 days on treatment. Patients without a valid clinical response assessment will be assigned a best overall response of NE. No response will be counted after PD.

Table 9 lists out the different scenarios of confirmed response based on subsequent assessment. The status of SD requires an on-study assessment at least 42 days on study. Patients without a valid clinical response assessment will be assigned a best overall response of NE.

Table 9 Confirmed Response Based on Subsequent Assessments*

First Time Point Response**	Second Time Point Response	Confirmed Response (Best Response)*
PD	No further evaluation	PD
NE	PD	PD
CR	PD	SD or PD (1)
PR	PD	SD or PD (1)
SD	PD	SD or PD (1)
CR	CR	CR
CR	NE **	SD or NE (2)
PR	CR	PR
PR	PR	PR
PR	SD (3)**	SD
PR	NE **	SD or NE (2)

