11.6.5 Progression-Free Survival (PFS)

Progression-free survival (PFS) is defined as the time from the first dose of study drug to the date of PD or death due to any cause, whichever occurs first in the absence of documented PD. PFS (in months) will be calculated as $(\text{first event date} - \text{first dose date} + 1)/30.4375$.

PFS will be summarized descriptively using the Kaplan-Meier estimate. The median, 25th percentile, and 75th percentile of PFS and their two-sided 95% CI (Brookmeyer & Crowley, 1982) will be calculated where appropriate. In addition, minimum and maximum will also be displayed. Kaplan-Meier plots will be provided for PFS.

Analysis will be performed on the FAS.

Censoring Rules for DoR and PFS

The following censoring rules will apply to event dates for time-to-event endpoints that are based on radiographic evaluations, i.e., DOR and PFS:

- Endpoints will be censored on the date of first dose (or randomization) with duration of 1 day under the following scenarios, unless patients die within 2 consecutive tumor assessments of first dose (on or prior to week 16, i.e. Cycle 5 Day 1 plus the 10 day window, which is Study Day 122 for Cohorts 1-8 or Day 136 for Cohort 9), in which case they will be assessed as having an event on the date of death (apply to PFS only):
 - baseline disease assessment inadequate to apply RECIST1.1;
 - no disease assessments are performed during study treatment; or
 - all disease assessments performed during study treatment result in the conclusion of NE.
- Endpoints will be censored on the date of the last evaluable disease assessment prior to the start of subsequent anti-cancer therapy under the following scenarios (apply to PFS and DOR). Last evaluable assessment date is defined as the last response assessment date on or after treatment start date with a response of CR, PR, or SD.
 - PD or death occur after ≥ 2 consecutive tumor assessments (i.e., ≥ 122 days of last evaluable tumor assessment for Cohorts 1-8 or ≥ 136 days for Cohort 9) that are missed or result in the conclusion of NE;
 - patient administered subsequent anti-cancer treatment prior to documented PD or death;
 - patient lost to follow-up;
 - patient withdrawal of consent for follow-up; or
 - patients alive and without PD at the time of analysis

Date of death will be considered an event for DOR and PFS only if death occurred in the absence of receiving subsequent anti-cancer therapy, and under one of the following scenarios:

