11.7.2 Adverse Events

AEs will be coded using Medical Dictionary for Regulatory Activities (MedDRA, Version 21.0). Non-serious AEs will be reported from the day of first dose of study treatment until at least 28 days after last administration of study drug treatment. Serious adverse events (SAEs) are reported from the time that the patient provides informed consent (i.e., prior to undergoing any study-specific procedure or assessment) until at least 28 days after last administration of study treatment. All SAEs ongoing or occur on Day 28 after the last dose should be followed until resolution or stabilization to a chronic condition, or administration of alternative cancer treatment, whichever is earlier.

Treatment-Emergent AEs (TEAEs)

Treatment emergent AEs (TEAEs) are AEs that begin after first dose of study treatment until 28 days after the last dose of study treatment and prior to the initiation of subsequent anti-cancer therapy.

Baseline signs and symptoms that change attribution or severity during the on-study period are TEAEs. Any ongoing TEAEs that changes in attribution or severity is captured as a new AE. All SAEs ongoing or occur on Day 28 after the last dose should be followed until resolution or stabilization to a chronic condition, or administration of alternative cancer treatment, whichever is later. All AEs will be coded according to the MedDRA Version 21.0 dictionary by system organ class (SOC), preferred term (PT), and severity grade using NCI CTCAE Version 5.0 .

Immune-related Adverse Event (irAE)

An irAE is defined as an AE that is associated with drug exposure and is consistent with an immune-mediated mechanism of action and where there is no clear alternate etiology. irAEs will be identified on the adverse events CRF page.

All adverse event summary tables will be based on the safety population. An overall summary of TEAEs by cohort will be presented.

A breakdown of the number and percentage of patients reporting each adverse event categorized by SOC and PT will be presented. Note that counting will be by patient not event and patients are only counted once within each SOC or PT at the highest grade. The following summaries will be presented:

- Treatment-emergent adverse events
- Treatment-related treatment-emergent adverse events
- Treatment-emergent adverse events leading to all study drug discontinuation
- Treatment-emergent serious adverse events
- Treatment-emergent adverse events resulting in death

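### SAP 9.2 sets an incomplete new-therapy date to the earliest compatible day without checking it against a documented progression, so a real PFS or DOR event can become a censoring

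*SAP*

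**What the plan says.** SAP 9.2 gives one rule per pattern of missingness:

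- Date fully missing, therapy known to have been given: "the start date will be set to last dose date + 1".
- Day and month missing, same year as the last dose: "then the last dose date + 1 will be assigned to the missing day and month". In a later year: "then Jan 1 will be assigned to the missing day and month".
- Day missing, month later than that of the last dose: "then the first day of the month will be assigned to the missing day". In the month of the last dose, the day after the last dose is used.

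No branch refers to a recorded progression, tumour assessment or follow-up contact. The resulting date is a cut-off in three places:

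- SAP 11.6.5 censors PFS and DOR at the last evaluable assessment before new therapy, and one listed trigger is "patient administered subsequent anti-cancer treatment prior to documented PD or death".
- SAP 11.6.1 takes best overall response (BOR) from assessments "recorded from the start of study drug until disease progression/recurrence, or start of anti-cancer therapy, whichever comes first".
- SAP 11.7.2 counts TEAEs "until 28 days after the last dose of study treatment and prior to the initiation of subsequent anti-cancer therapy". The on-treatment period in SAP 11.7 ends in the same way.

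Progression after the last dose is foreseen. Under footnote 11 of Protocol Table 1, patients who stop for reasons other than progression "will continue to have disease assessments at the same frequency until patient has radiologically confirmed progression, initiates a new anticancer therapy, or death".

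**The concern.** An earliest-date rule is harmless only if nothing on file contradicts it. Here something can. A patient stops for toxicity, stays on the scan calendar, progresses and then starts the next line, but the site records only a month or a year. The plan then treats the next line as if it began before the progression that probably prompted it. Because the patient is censored when progression is at hand, the censoring is informative.

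Incomplete dates are likely: subsequent therapies are collected every two months by telephone or email (Protocol Table 1, footnote 13), and SAP version 3.0 added a rule for fully missing dates. SAP 9.1 shows that a consistency check is feasible, since it tests an imputed AE or medication start date against the recorded stop date. SAP 9.2 has no counterpart.

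At stake are PFS and DOR, the completeness of the TEAE tables and, less certainly, confirmation of some responses.

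**Working it through.** The documents attach no figure to this rule, so the check applies the rule to dates and then asks how far the effect could reach.

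1. **A dated case (illustrative).** Last dose 3 March 2021, stopped for an adverse event. Scans on the 8-week calendar: 1 March SD, 26 April SD, 21 June PD (56 days apart). New therapy truly began on 28 June.
   - On file as June 2021: imputed 1 June, which precedes 21 June. PFS is censored at 26 April, 56 days before the PD.
   - On file as 2021, or nothing on file: imputed 4 March. PFS is censored at 1 March, 2 × 56 = 112 days before the PD.
   - A PD on or before the last dose is safe, because the imputed date is at least one day after the last dose.
   - Only PDs are converted. SAP 11.6.5 never counts a death after new therapy as an event, whatever the imputed date.

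2. **Direction.** Suppose n patients are at risk at the PD scan, d of them progress, and no other event falls between that scan and the earlier one. Moving one PD to a censoring at the earlier scan changes the Kaplan-Meier factor from 1 − d/n to 1 − (d−1)/(n−1). The gain is d/n − (d−1)/(n−1) = (n−d)/[n(n−1)], which is positive when d < n. The curve is higher from that scan on.

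3. **Day-only missing, month later than the last dose.** The PD is censored if it shares a calendar month with the therapy start and is not on the 1st. Assume PD dates uniform over 2020–2021 (24 months, 731 days) and therapy g days after PD. A month of length L contributes L − g − 1 such dates (zero if negative).
   - g = 7: 731 − 24×8 = 539; 539/731 = 0.737
   - g = 14: 731 − 24×15 = 371; 371/731 = 0.508
   - g = 21: 731 − 24×22 = 203; 203/731 = 0.278
   - g = 28: 14 months × 2 + 8 months × 1 = 36; 36/731 = 0.049

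   These shares apply only to patients with a PD after the last dose and a date missing only its day.

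4. **Imputation to last dose plus one.** Let f be the share who stop treatment before PD and m the share of incomplete dates, all imputed this way, with new therapy truly after PD. The share of PD events censored is then close to f × m. A simulation (exponential progression, median 120 days, 56-day scans, stopping time uniform before the PD scan) gave 1.4% at f = 0.15, m = 0.10 (product 1.5%) and 22.5% at f = 0.45, m = 0.50 (product 22.5%).

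   The Kaplan-Meier median was 168 days in all nine combinations of f and m. True survival is 2^(−112/120) = 0.524 at day 112 and 2^(−168/120) = 0.379 at day 168. The median therefore sits on the day-168 scan and would move only if the day-168 estimate rose above 0.5.

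5. **Safety tail.** Last dose plus one is day 1 of the 28 post-dose days, so all 28 are cut.

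6. **Response, only if the BOR cut-off also governs confirmation.** For Cohorts 1–4, P(success) = Σ(x = 1 to 9) C(9,x) p^x (1−p)^(9−x) × P(Bin(8,p) ≥ 3−x). This reproduces the stated type 1 error of 0.0466 at p = 0.05 and power of 0.9045 at p = 0.30; early termination is 0.95^9 = 0.63. If an assumed share q of responders lost confirmation, p = 0.30(1−q), and power would be 0.891 (q = 3%), 0.882 (5%), 0.855 (10%) or 0.787 (20%).

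**The case against.** The strongest reply concerns size. The documents do not say how many dates are incomplete. Treatment normally runs until progression and may continue beyond it, so many PDs fall on or before the last dose and are untouched. PFS and DOR are secondary and descriptive, and the simulated median did not move. All of this stands. The coarse scan grid explains the unmoved median, so it does not show absence of bias, but it does mean that material inflation has not been shown.

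A reader might infer from step 3 that about three-quarters of patients are affected. That figure is doubly conditional and falls to 4.9% at a 28-day gap.

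A reader might also infer that the rule lowers the primary endpoint. The new-therapy cut-off is in the BOR definition; the ORR sentence and Table 9 in SAP 11.6.1 do not say that a confirming scan must precede new therapy. If the cut-off does apply, an early date is conservative for a single-arm ORR.

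Finally, a reader might take any scan after the last dose as proof that new therapy had not begun. Footnote 11 is a scheduling instruction, and the SAP itself allows for later scans by restricting to assessments before new therapy. Flooring the primary rule at the last scan or contact could therefore credit a response obtained on the next-line drug. A floor at documented PD avoids that.

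The safety loss is also bounded. All AEs, including non-treatment-emergent ones, are listed, as are SAEs, and deaths are summarised and listed. Events leave the TEAE tables but stay in the report.

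**Conclusion.** The rule is wrong as written. Followed exactly, it can date new therapy before a PD already on file and turn that PFS or DOR event into a censoring one or more scan intervals earlier, biased towards longer PFS and DOR. When the imputed date is last dose plus one, the 28-day TEAE and on-treatment tail is lost. A confirming scan may also be lost, but only through the BOR window.

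Only patients with an incomplete date and a PD, confirming scan or adverse event on the wrong side of the imputed date are affected. Their number is unknown. The range of 1.4% to 22.5% of PD events rests on assumed stopping and missingness rates and on new therapy truly following PD. The effect on median PFS may be small. The documents support neither a claim that the medians are materially inflated nor one that ORR is necessarily reduced.

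**What to change.** In SAP 9.2, for efficacy, impute the start as the later of (a) the present rule's date and (b) the day after documented PD, capped at the end of the known month or year. In the dated case, June 2021, 2021 alone and a fully missing date all give 22 June, and the PD on 21 June counts. If May 2021 were on file, the cap gives 31 May, and the patient is still censored because the recorded month places therapy before the PD.

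For the TEAE and on-treatment windows, use the latest date compatible with the partial date.

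Report the number of imputed dates. As sensitivity analyses for PFS, DOR and ORR, run (i) the present rule and (ii) a floor at the last protocol tumour assessment or last contact recording no new therapy.

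The cost is SAP wording, a small change to the derivation and the extra runs; SAP 5.0 provides for an amended SAP before database lock. There are two downsides. The rule assumes that a recorded PD preceded the undated therapy, which run (i) tests, and efficacy and safety will use different imputed dates for the same patient, which the SAP should state openly.

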9.3 Imputation of Laboratory Values with Character Symbol

Missing laboratory data will not be imputed. However, laboratory values of the form of “< x” (i.e., below the lower limit of quantification) or “> x” (i.e., above the upper limit of quantification) will be imputed as “x” for the purpose of calculation of summary statistics and comparing to normal ranges. These values will still be displayed as “< x” or “> x” in the listings.

9.4 Protocol Deviations

Potential planned or unplanned protocol deviations noted during clinical monitoring will be documented by category (i.e., inclusion criteria, exclusion criteria, study drug, safety assessment, efficacy assessment, visit window, informed consent, prohibited medication, and other). All deviations will be reviewed, categorized, designated important or not important, and finalized prior to database lock. Important protocol deviations will be defined as those potentially impacting safety or efficacy assessments. Additional details of what will be considered important can be found in the Protocol Deviation Guidance document.

10.0 Interim Analyses

No interim statistical analysis is planned during this study. As detailed in Protocol Section 9.1, per the Predictive Probability Design, tumor responses in the clinical activity evaluable population will be reviewed and enrollment decisions will be documented.

11.0 Statistical Methods

All data collected during this study will be displayed in data listings, unless otherwise specified. Data listings will be sorted by cohort and patient identifier for safety and efficacy listings. In addition, listings will include all relevant derived variables.

Descriptive statistics (mean, median, standard deviations [STD], first quartile [Q1], third quartile [Q3], minimum and maximum values) for continuous variables will be presented. Mean and median will be presented to 1 decimal more than original data. STD will be presented to 2 decimals more than original data. Minimum and maximum will match the decimal points in the original data. For categorical variables, summary measures will include the frequency and percentage (with 1 decimal place) of patients in each category.

The summary tables will be presented by cohort (including initial and contingent cohorts) and for all cohorts combined.

Unless otherwise noted, missing data will not be imputed or carried forward.

All data summaries and tabulations will be prepared with SAS® Version 9.4 or higher.

11.1 Patient Disposition

The number and percentage of patients enrolled and treated in the study will be presented. The number and percentage of patients and each population to which they belong will be presented as well as the number and percentage of patients who withdrew from the study and a breakdown of the corresponding reasons for withdrawal and the number and percentage of patients who discontinued nivolumab, sitravatinib, pembrolizumab, or enfortumab with the corresponding reasons. Summaries will be reported by cohort. The number of patients enrolled by site and across sites will be presented. Disposition will be summarized descriptively by cohort and for all cohorts combined.

11.2 Important Protocol Deviations

Important protocol deviations for patients in the Enrolled Population will be reported by category. Important protocol deviations will be listed.

11.3 Demographic and Baseline Characteristics

Demographic and baseline data will be summarized descriptively by cohort and all cohorts combined for the initial and contingent cohorts for the Safety population. For continuous variables, descriptive statistics will include the mean, STD, median, Q1, Q3, and range. For categorical variables, descriptive statistics will include the number and percent.

The term “baseline” is defined as the last pre-dose assessment, (includes screening and Cycle 1 Day 1 pre-dose assessment which would represent a 29-day window), unless otherwise specified. Unscheduled visits assessments preceding C1D1 will be also considered for baseline. If assessment time is missing and there is no way to determine if the assessment occurred before or after study drug administration, Cycle 1 Day 1 assessments will be considered for baseline.

Demographic variables to be summarized include gender, reproductive status for female, race, ethnicity, age (years), baseline weight (kg), baseline height (m), baseline Eastern Cooperative Oncology Group (ECOG) status, and smoking history. Age is calculated from date of informed consent to date of birth.

Primary disease history will be tabulated for the Safety population and will include the summary statistics (count and percentage) for Disease Location (Renal Pelvis, Ureter, Bladder, or Urethra), disease stage (Unresectable Locally-Advanced or Metastatic), and Clinical Stage (III, IIIA, IIIB, IV, IVA, IVB, Stage unknown).

Demographic, primary disease history, and prior primary disease treatment data will be listed by patient.

Prior primary disease treatment (systemic therapies including platinum therapies and checkpoint inhibitors; radiotherapy, and surgery) will be tabulated for the Safety population and include the summary statistics (count and percentage) for the following:

- Prior platinum therapy - Platinum agent received (Cisplatin, Carboplatin, Other); Setting (Metastatic, Peri-operative); Disease Progression (Yes, No); Ineligible for platinum-based chemotherapy (Yes, No);
- Prior systemic therapy - Type (Neo-adjuvant or Adjuvant, Advanced Disease Treatment Regimen, Other);
- Prior checkpoint inhibitor – (Nivolumab, Pembrolizumab, Durvalumab, Atezolizumab, Avelumab, Other); Best Overall Response to prior Checkpoint inhibitor (CR, PR, SD, PD);
- Prior antibody drug conjugate – antibody drug conjugate received (Enfortumab Vedotin, Sacituzumab Govitecan);
- Prior radiotherapy – Type (Adjuvant, Palliative);
- Prior surgery – Location (Renal Pelvis, Ureter, Bladder, Urethra, Lung, Liver, Bone, Lymph Node, Other).

